## 6. Research Plan:

### **Protocol 1 (Aims 1-3)**

This prospective experimental study will include male and female adults with PD, as well as a control group consisting of healthy adults. We aim to recruit 30 participants in each group. We will recruit PD participants from the patient population at UF Fixel Institute for Neurological Diseases. Healthy control participants will be recruited from the community population, including spouses and caregivers of PD participants, as well as HealthStreet. All participants will provide written consent before enrollment into the study, which will be approved by Institutional Review Board (IRB) at the University of Florida.

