## **Statistical Analysis**

**Aim 1:** A multiple regression analysis will be conducted with the slope magnitude estimation as the outcome and disease duration, age, and sex as the independent variables in addition to their mutual interaction terms. Model selection technique will be adopted to select the optimal parsimonial model deemed for the data. We will also perform subgroup analysis to

compare the slope magnitude estimation between PD patients with PAS (penetration-aspiration scale) no more than 2 and PD patients with PAS greater than 2 by adjusting confounding factors of age, gender and BMI, etc. to demonstrate that reduced slope of magnitude estimation is present in PD patients regardless of PAS status. We will include other swallow and cough outcome variables in this model to determine relationships between dependent variables.

**Aims 2 and 3:** We will first fit a multiple regression model with P1 and N2 peak amplitude and gating ratios as the dependent variable and condition (1 = attend and 2 = ignore) as independent variables by controlling confounding variables including age, gender, BMI, etc. In order to determine the relationship between P1 and N2 peaks and swallow and cough function, we will fit a second multiple regression model with P1 and N2 (amplitude and gating ratio), cough and swallow outcomes as the dependent variables and disease duration as the primary independent variable by controlling confounding variables including age, gender, BMI, etc. Also, model selection technique will be adopted to select the optimal model. Besides the primary outcomes of P1 and N2 peaks, other secondary outcomes such as N1 and P2 amplitudes and gating ratios will be analyzed.

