### **Protocol 2 (aim 4)**

**Participants:** This study will include men and women with PD, and we will recruit from those participating in protocol 1, in addition to the general PD population at UF Fixel Institute for Neurological diseases given protocol 2's larger required N. For participants who did complete protocol 1, the procedures will not be replicated in protocol 2 (therefore these participants would only complete the 2nd and 3rd protocol 2 visits). The inclusionary and exclusionary criteria will be identical to those of protocol 1, with the exception that this protocol will also include people with possible or probable progressive supranuclear palsy (PSP) or multiple systems atrophy (MSA).

**Power Analysis:** To test the hypothesis that the relationship between swallow and cough motor deficits, and reflex cough sensitivity varies as a function of disease duration in PD, we would compare the penetration/aspiration scale change from baseline with 10 to 18 months apart for PD patients. As shown in our pilot study data, the mean (SD) penetration-aspiration scale change from baseline for the first two 10 to 14 months period are 2.08 (1.97) and 2.82 (2.33), respectively. Based on it, to reach a 0.85 power by controlling the type I error rate to 0.05 for detecting this effect size with two-sided test, we would need 155 PD patients.

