### **Procedures to be included from protocol 1 (See protocol 1 for complete description of these procedures)**

Pulmonary function, depression and apathy, Reflex and voluntary cough procedures, Swallowing evaluation procedures will be completed in a manner identical to that described in the preceding paragraphs.

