**Statistical analysis:** In the statistical analysis, we would fit a linear mixed effects model to take into account the repeated measurement by regarding each subject as a cluster. Specifically, in the analysis, the repeatedly measured outcome, i.e. change of penetration-aspiration scale scores (PAS), C2, cough and swallowing physiology variables from baseline, will be fitted by adjusting for fixed effects terms including baseline PAS, age, sex, medications, levodopa equivalent dose, surgical status, and disease duration (2=third 10-18 month; 1=second 10-18 month; and 0=first 10-18 month) and the random effects term due to participants. Restricted resampling model selection (Zou et al. 2015) technique will be adopted to conduct the valid statistical inference for repeated measurement data and it is also robust to missing data which is particularly useful for this study. **Expected outcomes:** Results of this aim are expected to provide a clinical deliverable in the form of sensitive and specific predictor(s) of airway protection dysfunction that are more customized for patients with different PD durations. As well, because of the study's prospective longitudinal design, this study will also be the first to examine the natural history of cough function in people with PD over the proposed 3-year time period.

**Data storage:** All participant records will be maintained in HIPPA compliant storage. Paper copies of the ICF will be kept in a locked cabinet, in the locked research laboratory of the PI (D2-063 or DG-143; [name]). Paper data collection forms will be kept in a separate, locked file cabinet, also in the research laboratory of the PI. Paper forms will not include participant names or dates; rather participants will be assigned a unique participant ID number that will be kept separate from the name. Electronic database files containing summary data for individual participants and compiled data for all participants will be saved according to participant number within a limited access, password protected folder on the PI's P-drive.

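### The regressions of cough and swallow outcomes on disease duration rest on 30 PD patients, although identical first-visit measures on about 155 are never related to years since diagnosis

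*Combined protocol and SAP*

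**What the plan says.** **Protocol 1.** The recruitment target is "We aim to recruit 30 participants in each group", meaning PD and healthy controls. Under Statistical Analysis, the second model for Aims 2 and 3 takes P1 and N2 measures together with "cough and swallow outcomes as the dependent variables and disease duration as the primary independent variable", adjusted "by controlling confounding variables including age, gender, BMI, etc". No analysis set is named. The Aim 1 model is different: its outcome is the slope of magnitude estimation for inspiratory loads. Of the cough and swallow variables it says only: "We will include other swallow and cough outcome variables in this model to determine relationships between dependent variables".

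**Protocol 2.** The power analysis concludes that "we would need 155 PD patients". Eligibility matches Protocol 1 except that PSP and MSA are also admitted. The procedures carried over are pulmonary function, depression and apathy, reflex and voluntary cough, and swallowing: "Swallowing evaluation procedures will be completed in a manner identical to that described in the preceding paragraphs". Loads and SEP are not carried over. Protocol 1 cough and swallow data serve as the first time point for patients in both protocols. No reuse in the other direction is described.

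**Protocol 2 model.** The outcomes are changes in PAS, C2, "cough and swallowing physiology variables from baseline, will be fitted by adjusting for fixed effects terms including baseline PAS" and other terms. Disease duration in this model takes the values 0, 1 and 2 for successive 10-18 month intervals of the study.

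**The concern.** Disease duration is undefined for healthy controls, so at most 30 people inform the motor-on-duration slopes in Protocol 1. Protocol 2 collects the same outcomes at a first visit in a sample about five times as large. Its model subtracts those values as the baseline and enters baseline PAS as a covariate. Neither step estimates how the level of a cough or swallow measure varies with years since diagnosis.

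Hypothesis 1 is a statement about timing: blunted sensation at 0-5 years, ahead of cough or swallowing dysfunction, with the two related by 6-10 years. Part of that claim is that motor function is still preserved early. With 30 patients spread over all durations, a flat or non-significant motor curve cannot separate preserved function from a decline too small to detect, and that ambiguity favours the hypothesis.

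**Working it through.** **1. The plan's own figure.** No sample-size calculation is given for Protocol 1, so only the 155 can be checked. Inputs (Protocol 2, Power Analysis): mean PAS changes 2.08 (SD 1.97) and 2.82 (SD 2.33), and "to reach a 0.85 power by controlling the type I error rate to 0.05 for detecting this effect size with two-sided test".
- Difference: 2.82 - 2.08 = 0.74.
- SD of the paired difference with zero within-patient correlation: sqrt(1.97² + 2.33²) = 3.051.
- A paired t-test then needs 154.6, rounded up to 155. The figure is reproduced as a total number of PD patients.

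**2. Information in the slopes.** The slope standard error is proportional to 1/sqrt(n) when duration spread and residual variance are alike in both samples.
- n = 30 against n = 155: sqrt(155/30) = 2.27.
- Share of the first-visit information left unused: 1 - 30/155 = 81%.

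**3. Detectable partial correlation.** Adjusting for age, sex and BMI (three covariates), Fisher's z has SE = 1/sqrt(n - 6). The value detectable at 80% power, two-sided 0.05, is tanh[(1.960 + 0.842)/sqrt(n - 6)].
- n = 30: tanh(2.802/4.899) = 0.52. A noncentral t on n - 5 residual degrees of freedom gives 0.50.
- n = 155: tanh(2.802/12.207) = 0.23. The noncentral t gives 0.22.

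**4. Power and interval at an assumed partial correlation of 0.30.** This value is an assumption; the documents give none.

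| PD first visits | SE gain over n = 30 | Detectable r (Fisher z) | Power at r = 0.30 | 95% CI around 0.30 |
|---|---|---|---|---|
| 30 | 1.0 | 0.52 | 0.33 | -0.09 to 0.61 |
| 100 | 1.8 | 0.28 | 0.85-0.86 | 0.11 to 0.47 |
| 125 | 2.0 | 0.25 | 0.92-0.93 | 0.13 to 0.45 |
| 155 | 2.3 | 0.23 | 0.97 | 0.15 to 0.44 |
| 185 | 2.5 | 0.21 | 0.99 | 0.16 to 0.43 |

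The rows cover what the plan leaves open. The number of the 155 who come from Protocol 1 is not given (185 means no overlap). Nor is the number of PSP or MSA participants, who must be left out, or the number of unusable visits (100 and 125 are illustrative).

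**5. The timing contrast.** Sensation is measured in Protocol 1 only, so the sensory half stays at 30. In units of the n = 30 standard error, with equal standardised variances:
- Uncorrelated estimates: sqrt(1 + 1) = 1.41 falls to sqrt(1 + 30/155) = 1.09, a reduction of about 23%.
- Assumed within-patient correlation 0.4, with the 30 nested in the 155: sqrt(2 - 0.8) = 1.10 falls to sqrt(1 + 30/155 - 0.8 × 30/155) = 1.02, a reduction of about 7%.

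**The case against.** **The joint model has a purpose.** The second model is introduced to relate P1 and N2 to cough and swallow function. Fitting sensory and motor outcomes on duration in the same patients is coherent, and moving the motor equations to another sample would make the curves harder to compare. This stands, and it is why the pooled fit should be added and the Protocol 1 fit kept.

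**The restriction to 30 is inferred.** It follows from where the text sits and from the one-way reuse of data; the plan does not state it. This is true, but it leaves the analysis set open until after data are seen, which is itself a reason to write it down.

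**Aim 4 already owns the large-sample question.** Hypothesis 4 and the Protocol 2 power rationale do point to disease duration. The specified Protocol 2 model, however, contains no term for years since diagnosis and no outcome expressed as a level, so it does not supply these curves.

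**Analysing a self-contained protocol on its own participants is not an error.** Agreed. The point is one of efficiency and of what a null motor result could mean.

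**Stronger readings the documents do not support.** A reader might infer that Aim 1 as a whole could be fitted to 155 patients. It could not: its outcome is the load slope, measured only in Protocol 1, and the section contains no separate cough-on-swallow equation to pool. A reader might also infer that the whole test of sensation preceding motor decline becomes 2.3 times as precise. Step 5 shows a reduction of about 23% or less under its assumptions, and any comparison with healthy people remains limited by the 30 controls.

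**Conclusion.** The concern holds for one set of equations: each cough and swallow outcome regressed on years since diagnosis. For these, the plan as placed uses about a fifth of the PD first-visit data that the two protocols will hold, and the standard error could fall by a factor of about 2.3. At 30 patients, only partial correlations of about 0.5 or more are detectable with 80% power, and an assumed 0.30 would be missed two times in three. Even with 100 usable first visits, power at 0.30 would be about 0.86.

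The standard-error ratio does not depend on the assumed correlation. It does assume similar duration spread and residual variance in the two samples, which common recruitment at one institute and near-identical eligibility make plausible but do not guarantee. The load-slope, SEP, sensory-to-motor and control comparisons are unaffected. It would also go too far to say that Protocol 2 first-visit data are unused: they define the changes analysed there, and baseline PAS is a covariate.

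**What to change.** In the Protocol 1 Statistical Analysis, under Aims 2 and 3, state that:
- each cough and swallow outcome is also regressed on years since diagnosis using the first-visit data of all PD participants from both protocols, with one record per patient and PSP/MSA excluded;
- the model adjusts for age and sex, for BMI where recorded (the Protocol 2 model does not name it), and includes a protocol indicator;
- conclusions about when cough or swallow dysfunction appears are drawn from this pooled fit;
- the 30-patient Protocol 1 fit is kept for comparison with the load and SEP duration curves in the same people.

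This needs no new patients, visits or procedures. The cost is that the pooled fit is final only once Protocol 2 first visits are complete; Protocol 1 results for the load and SEP measures need not wait.

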### **Protocol 2 (aim 4)**

**Participants:** This study will include men and women with PD, and we will recruit from those participating in protocol 1, in addition to the general PD population at UF Fixel Institute for Neurological diseases given protocol 2's larger required N. For participants who did complete protocol 1, the procedures will not be replicated in protocol 2 (therefore these participants would only complete the 2nd and 3rd protocol 2 visits). The inclusionary and exclusionary criteria will be identical to those of protocol 1, with the exception that this protocol will also include people with possible or probable progressive supranuclear palsy (PSP) or multiple systems atrophy (MSA).

**Power Analysis:** To test the hypothesis that the relationship between swallow and cough motor deficits, and reflex cough sensitivity varies as a function of disease duration in PD, we would compare the penetration/aspiration scale change from baseline with 10 to 18 months apart for PD patients. As shown in our pilot study data, the mean (SD) penetration-aspiration scale change from baseline for the first two 10 to 14 months period are 2.08 (1.97) and 2.82 (2.33), respectively. Based on it, to reach a 0.85 power by controlling the type I error rate to 0.05 for detecting this effect size with two-sided test, we would need 155 PD patients.

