## **5. Specific Aims:**

The specific aims for this project are:

Aim 1: To determine the relationships between blunted airway somatosensation, reflex cough sensitivity and effectiveness, and swallowing function in people with PD.

Hypothesis 1: We predict that blunted airway somatosensation will appear earlier (years 0 – 5 post-diagnosis) in the disease process than either cough or swallowing dysfunction, and that by 6-10 years post-diagnosis, blunted respiratory somatosensation will correlate with reduced reflexive cough sensitivity and effectiveness, and decline in swallow function and safety.

Specific aim 2: To determine whether measures of discriminative and affective processing of general airway sensation is/are associated with deficits in reflex cough and swallowing function in people with PD.

Hypothesis 2: People with PD will exhibit reduced discriminative processing components of airway stimuli. With disease progression, measures of affective processing components will decline and this will directly correlate with diminished reflex cough sensitivity and swallowing function.

Specific aim 3: To determine whether over-filtering of airway stimuli is associated with swallowing or cough deficits in people with PD.

Hypothesis 3: Over-filtering of airway stimuli will be associated with deficits in reflex cough and swallowing function in people with PD.

Aim 4: Determine the relationships between observable motor aspects of swallowing, cough, and cough sensitivity over a 3-year time period in people with PD.

Hypothesis 4: Swallowing safety and physiology in people with PD will exhibit significant differences over 3 time points, spaced 10 – 18 months apart. For people within 9 years of PD diagnosis, reduced reflex cough sensitivity will not be a sensitive and/or specific indicator of swallowing dysfunction. However, for those with a greater disease duration (10+ years), reflex cough sensitivity will be a sensitive and specific biomarker of swallowing dysfunction.

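### The 0.85 power with 155 patients is attached to the disease-duration hypothesis but computed for a PAS-change contrast, and the biomarker part of Hypothesis 4 has no analysis or precision basis

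*Combined protocol and SAP*

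**What the plan says.** Hypothesis 4 (Section 5, Specific Aims) has two parts. The first concerns change over time: "Swallowing safety and physiology in people with PD will exhibit significant differences over 3 time points". The second concerns diagnostic value by time since diagnosis. Within 9 years, reduced reflex cough sensitivity is expected not to be a good indicator of swallowing dysfunction, but "for those with a greater disease duration (10+ years), reflex cough sensitivity will be a sensitive and specific biomarker of swallowing dysfunction".

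The Power Analysis (Section 6, Protocol 2) opens with its purpose: "To test the hypothesis that the relationship between swallow and cough motor deficits, and reflex cough sensitivity varies as a function of disease duration". It then turns to PAS change and gives pilot values: "the mean (SD) penetration-aspiration scale change from baseline for the first two 10 to 14 months period are 2.08 (1.97) and 2.82 (2.33"). From these it derives 155 PD patients, "to reach a 0.85 power by controlling the type I error rate to 0.05 for detecting this effect size with two-sided test". It names no test, within-patient correlation or allowance for dropout.

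The Protocol 2 Statistical analysis is a linear mixed model with a participant random effect. On the outcome side it lists "change of penetration-aspiration scale scores (PAS), C2, cough and swallowing physiology variables from baseline, will be fitted by adjusting for fixed effects terms". The adjustment set is "fixed effects terms including baseline PAS, age, sex, medications, levodopa equivalent dose, surgical status, and disease duration", and the last of these is coded as "disease duration (2=third 10-18 month; 1=second 10-18 month; and 0=first 10-18 month"). The Expected outcomes text that follows promises predictors of airway protection dysfunction with good sensitivity and specificity, tailored to different PD durations.

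**The concern.** The hypothesis named in the power paragraph is one of effect modification: does the relation between cough sensitivity and motor deficit depend on how long the patient has had PD? A difference in mean PAS change between two follow-ups cannot answer that, because neither cough sensitivity nor time since diagnosis enters it. This is the only power statement in the protocol.

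As written, a positive or negative biomarker result by disease duration could be reported as coming from a study with 85% power for that question, although its precision was never considered. Because no accuracy analysis is specified, the cough cut-off, the visit used and the definition of swallowing dysfunction could all be chosen after the data are seen. That affects the main clinical deliverable promised for this aim.

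**Working it through.** **1. Reproducing the 155.** Inputs from the Power Analysis: means 2.08 and 2.82, SDs 1.97 and 2.33, power 0.85, two-sided alpha 0.05.

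- Difference: 2.82 − 2.08 = 0.74.
- SD of the within-patient difference: √(1.97² + 2.33² − 2r × 1.97 × 2.33), where r is the correlation between the two changes. The documents do not give r.
- At r = 0: √(3.8809 + 5.4289) = 3.051, so the standardised difference is 0.74 / 3.051 = 0.2425.
- Paired t-test, noncentral t with noncentrality 0.2425 × √155 = 3.02 on 154 degrees of freedom: power 0.851. With 154 patients it is 0.849. So 155 is the smallest number that reaches 0.85.

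**2. How the figure moves with r (assumed values).**

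| r | SD of difference | Power at 155 | N for 0.85 |
|---|---|---|---|
| 0 | 3.051 | 0.851 | 155 |
| 0.2 | 2.734 | 0.918 | 125 |
| 0.5 | 2.172 | 0.988 | 80 |

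Both changes are measured from the same baseline score, which tends to make r positive. Zero is therefore probably a cautious choice, but the plan should say that it was made.

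**3. What the calculation covers.** Setting Hypothesis 4 beside the power inputs and the model:

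| Part of Hypothesis 4 | In the power calculation? | In the mixed model? |
|---|---|---|
| Swallowing differs over three time points | Yes, PAS change at two follow-ups | Yes, through the period term |
| Cough sensitivity is not a good indicator within 9 years | No | No |
| Cough sensitivity is a good biomarker at 10+ years | No | No |

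Three features of the model explain the last two rows. C2 is an outcome, and no cough measure is among the listed fixed effects. The term called disease duration takes the values 0, 1 and 2 for successive follow-up periods; it is not years since diagnosis. No cut-off, definition of swallowing dysfunction for this test, interaction with years since diagnosis, sensitivity, specificity or AUC is specified. The promised model selection chooses among terms, which does not produce diagnostic accuracy by duration group.

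**4. What precision would require (illustration only).** The documents do not give the number of Protocol 2 patients expected at 10+ years, or how many of them will have dysfunction. Assume a true sensitivity p = 0.80 and one observation per patient. The Wilson 95% half-width, with z = 1.96, is

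z√(p(1 − p)/n + z²/(4n²)) / (1 + z²/n).

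| Target half-width | Patients with dysfunction needed in the group | Half-width reached |
|---|---|---|
| 0.20 | 14 | 0.197 |
| 0.15 | 26 | 0.149 |
| 0.10 | 60 | 0.0998 |

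The same counts, among patients without dysfunction, apply to a specificity of 0.80.

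**The case against.** The strongest defence is that the power paragraph is open about what it sizes. It states that PAS change will be compared and gives power for that effect size, and nowhere does it claim 0.85 for sensitivity or specificity. Sizing a study on one quantifiable contrast is ordinary practice, and this contrast does serve the first sentence of Hypothesis 4. All of that stands. It does not rescue the opening sentence, which ties the calculation to the duration hypothesis, and it does not supply the missing analysis. The regressions on disease duration in the Statistical Analysis for Aims 1 to 3 belong to Protocol 1. The PAS split there compares load-magnitude slopes and does not assess cough sensitivity as a classifier.

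A reader might infer more than the documents support in four ways.

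- **That 155 is miscalculated.** It is not; it reproduces exactly under a paired test at zero correlation.
- **That the unnamed test leaves the PAS contrast seriously underpowered, as if 155 were divided between two independent groups.** The design measures each patient at three time points and the model treats the patient as a cluster, so that reading is excluded. A negative correlation would lower power, but it is unlikely for two changes that share a baseline.
- **That years since diagnosis is not collected.** The lists of disease-status items do not name it. However, participants complete a health history questionnaire (Appendix 1) that is not in the supplied text, so this cannot be settled.
- **That 155 is too few for the biomarker question.** The group sizes and the frequency of dysfunction are not given, so no shortfall can be shown.

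**Conclusion.** The point holds as a mismatch between hypothesis, power and analysis. The 0.85 is sound for the second-versus-first follow-up PAS change if the test is paired and the correlation is zero, and it is higher if the correlation is positive (0.92 at an assumed 0.2). It gives no information about the within-9 versus 10+ year biomarker claim. Following the plan as written would leave that part of Hypothesis 4 untested, while the power paragraph implies that it is covered at 85%. The conclusion about coverage rests on the text alone. The correlations and the 80% accuracy are assumptions used to show scale. This should be corrected, but it is no reason to change the sample size.

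**What to change.** N stays at 155.

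1. **Power Analysis.** State that 0.85 is the power to detect the difference in PAS change from baseline between the second and first follow-ups. Name the paired test and the zero-correlation assumption. Remove the statement that this tests the disease-duration hypothesis.
2. **Protocol 2 Statistical analysis.** Add a sensitivity and specificity (or AUC) analysis of C2 or the urge-to-cough (UtC) slope for swallowing dysfunction, by years since diagnosis (within 9 versus 10+). Keep that variable separate from the follow-up-period term. Define dysfunction in advance, for example by the PAS above 2 split already used for Aim 1, and fix the cough cut-off and the visit. Report 95% confidence intervals and label this part as estimation, not powered. If visits are pooled, the intervals must allow for repeated observations on the same patient.
3. **Data items.** Confirm that years since diagnosis is captured.

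The cost is one paragraph reworded and one added, using C2, UtC and PAS data already planned. The protocol loses its claim to 85% power for the duration hypothesis, and the intervals in the 10+ year group may prove wide.
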